#### PROJECT SUMMARY

Trigeminal neurostimulation of the dorsal anterior mucosal surface of the tongue has been proposed to treat a variety of pathologies and to promote neuro-muscular coordination and rehabilitation.

ULFTENS dental can also be considered a form of trigeminal neurostimulation applied to the skin surface bilaterally at the level of the tragus. With the latter mode of administration, there are central effects that can be evidenced at the level of pupil size (7,8), on the descending circuits that modulate pain, probably also on the centers that control arousal (9) and autonomic response under stress conditions monitored by HRV (10). The sensory component of the tongue is particularly developed, and the tongue itself is involved through its senses in a more complex modulation of sensory afferents than the tragus area, The aim of our project is to evaluate and compare the effects on two parameters of Heart Rate Variability (Low frequency, LF and Root Mean square standard deviation, RMSSD) in healthy women after 30 minutes of trigeminal electrical stimulation with dental ULF-TENS at the level of the dorsal anterior surface of the lingual mucosa or at the level of the tragus.

#### AIMS AND OBJECTIVES OF THE STUDY

In this work, we aim to test through the HRV collected with the PPG (Photoplethysmography) signal the possibility that trigeminal stimulation at the level of the dorsal anterior mucosal surface of the tongue is different than trigeminal stimulation performed bilaterally at the level of the tragus using ULF sensory TENS odontoid.

Should the hypothesis be confirmed, this type of stimulation could find its indication in clinical cases, especially chronic and difficult to manage, in which an imbalance of the centers controlling the autonomic stress response and the centers responsible for modulating arousal has been suggested, including some types of chronic TMD.

### STUDY DESIGN.

This research is a randomized, open-label, parallel-group clinical trial (interventional study). The population examined will be patients, aged 18-30 years old female from the Department of Orthodontics at the University of L'Aquila. The study will be performed in the same department. Patients participating in the study will be selected according to the exclusion and inclusion criteria. The exclusion criteria are: presence of acute and/or chronic cardio-circulatory and respiratory disorders, metabolic and autonomic system disorders, intake of excitatory or inhibiting substances of the peripheral and central nervous system, presence of generalised anxiety and/or panic attacks or mood disorders. All female patients aged 18-30 years will be included in the study. The selected patients will be randomly divided into two groups by means of randomization software downloaded into a computer.

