#### **METHODOLOGY**

The research protocol involves the following procedure: Patients will be randomly divided into cases (TUD group) and controls (tragus group)following an online randomization software. Recordings will be made in the morning, the patient will be made to lie on a medical examination chair for a total of 30 minutes. Patients in the TUD group will be given a stimulation device to be inserted on the dorsal mucosa of the tongue and connected to TENS, while the control group will have two electrodes placed at the level of the tragus and also connected to TENS. Sensors for assessing Heart rate variability using a photoplethysmograph will also

be placed on the index finger of the hands. The photoplethysmographic wave will assess two parameters of HRV: the Low Frequencies (LF) and RMSSD. For the first 6 minutes of recording, the photoplethysmographic wave of HRV in the absence of stimulation will be calculated, then both case and control groups will be activated stimulation with TENS at the level of the tongue and tragus respectively. HRV under stimulation for another 6 minutes will be re-evaluated again. Finally TENS will be turned offand HRV wave after stimulation will be evaluated for the last time.

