#### **Statistics**

**Descriptive Statistics:** 

Demographic and baseline characteristics will be summarized using means, standard deviations, medians, and interquartile ranges for continuous variables, and frequencies and percentages for categorical variables.

Primary Outcome Analysis:

The primary outcome will be analyzed using an independent t-test (or Mann-Whitney U test if data are not normally distributed) to compare the intervention and control groups. Changes from baseline to post-intervention will be analyzed using paired t-tests (or Wilcoxon signed-rank tests if data are not normally distributed) within each group.

Secondary Outcome Analysis:

If secondary outcomes are included, similar statistical methods will be applied as appropriate based on the type of data (e.g., chi-square tests for categorical outcomes, ANOVA for continuous outcomes with more than two groups).

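### The open-label plan neither masks nor fixes the derivation of LF and RMSSD from the PPG recordings, so nothing prevents processing choices being made with the arm known

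*Combined protocol and SAP*

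**What the plan says.** The Study Design section gives the blinding status once, without qualification: "This research is a randomized, open-label, parallel-group clinical trial (interventional study". No section mentions a masked assessor, coded recordings or a blinded analysis.

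The Methodology section defines the outcomes: "The photoplethysmographic wave will assess two parameters of HRV: the Low Frequencies (LF) and RMSSD". It describes three recordings:

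- Baseline: "For the first 6 minutes of recording, the photoplethysmographic wave of HRV in the absence of stimulation will be calculated".
- During stimulation: "HRV under stimulation for another 6 minutes will be re-evaluated again".
- After stimulation: "HRV wave after stimulation will be evaluated for the last time".

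The arms differ visibly. "Patients in the TUD group will be given a stimulation device to be inserted on the dorsal mucosa of the tongue", while the control group has electrodes at the tragus. The PPG sensor is on the index finger in both arms.

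The Statistics section says the primary comparison uses an "independent t-test (or Mann-Whitney U test if data are not normally distributed". It gives no criterion for judging normality.

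**The concern.** Participants and the operator cannot readily be masked to tongue versus tragus, and that is a fair reason to run the session open. The reason does not carry over to the later step in which a stored wave becomes an LF or RMSSD value. That step can be separated from the session, because the finger sensor is the same in both arms and a saved file need not show the allocation.

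The instrument delivers the raw wave. LF and RMSSD are calculated from beat intervals within a chosen window. RMSSD is built from successive differences, so a few misdetected or retained beats can change it. Someone, or some software setting, decides which minutes count and which beats or recordings are usable. If those decisions are made with the arm known and differ between arms, they shift the between-arm difference. Randomisation gives no protection against that, because the decisions come after allocation.

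**Working it through.** **1. What the protocol fixes and what it leaves open**

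| Step | Fixed | Open |
|---|---|---|
| Baseline window | First 6 minutes, no stimulation | Who calculates the values |
| Stimulation window | 6 minutes | When it starts after TENS is switched on; who calculates |
| Post-stimulation window | Follows TENS being switched off | Length; who calculates |
| Artefacts and unusable recordings | Nothing | Software, beat editing, exclusion rule |
| Between-group test | t-test or Mann-Whitney U | Criterion for choosing; whether the choice is made with the arm known |

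The start of the stimulation window is harder to infer because two sections differ on timing. The Project Summary describes effects after 30 minutes of stimulation. The Methodology section has the patient lying for 30 minutes in total, which includes the 6-minute unstimulated baseline. These passages need to be reconciled.

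**2. What an arm-dependent shift would do**

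The documents give no sample size, SD, alpha or effect size, so there is no figure of the plan's own to reproduce. The inputs below are all assumptions:

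- two-sided alpha of 0.05 and no true difference between arms;
- a spurious shift *b* in the between-arm difference of 0, 0.1, 0.2 or 0.3 SD;
- *n* = 20 or 30 per arm.

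The false-positive rate is the rejection probability of a two-sample t-test with 2*n* − 2 degrees of freedom and non-centrality δ = *b* × √(*n*/2).

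For example, with *n* = 20 and *b* = 0.3, δ = 0.3 × √10 = 0.949. With 38 degrees of freedom the critical value is 2.024, and the rejection probability is 0.152.

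| Shift *b* (SD) | 20 per arm | 30 per arm |
|---|---|---|
| 0 | 0.050 | 0.050 |
| 0.1 | 0.061 | 0.067 |
| 0.2 | 0.095 | 0.119 |
| 0.3 | 0.152 | 0.208 |

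A normal approximation, Φ(δ − 1.96) + Φ(−δ − 1.96), agrees closely: 0.062, 0.097 and 0.158 at 20 per arm, and 0.067, 0.121 and 0.213 at 30 per arm.

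The zero row is what fully automatic processing with fixed settings would give. Nothing in the documents says which row applies.

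**The case against.** The strongest reply is that LF and RMSSD are instrument-derived, that no manual editing is described, and that the baseline and stimulation recordings each have a stated length of 6 minutes. If software computes everything with fixed settings, knowledge of the arm cannot alter a value. This stands as a condition: it would bring the risk close to zero. The protocol does not say that the condition is met.

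Several stronger readings are tempting, and the documents do not support them:

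- *That the people deriving the values know the arm.* This is an inference from an unqualified open-label statement plus silence. The Methodology section does not say who derives the values or what they know.
- *That a bias exists.* It would need discretion that is used differently by arm, and no such discretion is documented.
- *That the Expected Results section gives the bias a direction.* It predicts improved HRV parameters but names no arm, and both arms are stimulated. The Aims section says only that the two sites differ.
- *That coded files would remove bias altogether.* They act on processing and analysis only. Participant expectation and operator behaviour during the session remain, and coding may be incomplete if stimulation leaves an arm-specific trace in the signal.

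It is also fair to say that unspecified windows are a defect of outcome definition, separate from masking. Fixed rules alone would deal with much of the risk. The two safeguards work together: fixed rules narrow the discretion, and coding protects whatever discretion is left, including the decision to exclude a recording.

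**Conclusion.** The point holds as an unaddressed and avoidable risk of bias in the tongue-minus-tragus comparison. The open-label statement is unqualified, no masking of derivation or analysis is planned, and no artefact rule or complete window definition limits the choices available.

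Its size cannot be established from the documents. Under the assumptions in the working, the false-positive rate runs from 5% with no shift up to about 15% at 20 per arm or 21% at 30 per arm with a 0.3 SD shift. The change should be made before any recording is processed, because values already derived with the arm known cannot be masked afterwards.

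**What to change.** In the Study Design and Methodology sections, state that participants and the operator are unmasked but that processing and analysis are masked, and then:

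1. Save each PPG recording under a code that does not show the arm.
2. Prespecify one set of settings for all recordings: the start and length of each window, the artefact and beat-editing rule, and the criterion for excluding a recording. Say whether derivation is fully automatic.
3. Derive LF and RMSSD for every epoch with those settings, and lock the table and any exclusions before merging the allocation list.
4. In the Statistics section, fix the between-group test in advance, or choose it with the arms labelled only A and B. Without this step, the choice of test would still be made after allocation is merged.

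The cost is modest. A team member other than the processor has to hold the code list, and results by arm are available slightly later. The documents describe no staffing, so the sponsor should confirm that an existing member can take this on. No extra participants, visits or procedures are needed.

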#### **METHODOLOGY**

The research protocol involves the following procedure: Patients will be randomly divided into cases (TUD group) and controls (tragus group)following an online randomization software. Recordings will be made in the morning, the patient will be made to lie on a medical examination chair for a total of 30 minutes. Patients in the TUD group will be given a stimulation device to be inserted on the dorsal mucosa of the tongue and connected to TENS, while the control group will have two electrodes placed at the level of the tragus and also connected to TENS. Sensors for assessing Heart rate variability using a photoplethysmograph will also

be placed on the index finger of the hands. The photoplethysmographic wave will assess two parameters of HRV: the Low Frequencies (LF) and RMSSD. For the first 6 minutes of recording, the photoplethysmographic wave of HRV in the absence of stimulation will be calculated, then both case and control groups will be activated stimulation with TENS at the level of the tongue and tragus respectively. HRV under stimulation for another 6 minutes will be re-evaluated again. Finally TENS will be turned offand HRV wave after stimulation will be evaluated for the last time.

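### HRV is recorded before, during and after stimulation, but no stated test names the under-stimulation recording and the between-arm test does not adjust for baseline

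*Combined protocol and SAP*

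**What the plan says.** The Methodology section describes three recordings in the same person. The first is unstimulated: "For the first 6 minutes of recording, the photoplethysmographic wave of HRV in the absence of stimulation will be calculated". The second is made with TENS on: "HRV under stimulation for another 6 minutes will be re-evaluated again". The third follows switch-off: "HRV wave after stimulation will be evaluated for the last time"; its length is not given. Two measures are taken from each recording: "The photoplethysmographic wave will assess two parameters of HRV: the Low Frequencies (LF) and RMSSD".

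In the Statistics section, under Primary Outcome Analysis, the between-arm comparison reads "The primary outcome will be analyzed using an independent t-test (or Mann-Whitney U test if data are not normally distributed". No parameter, epoch or change score is attached to it. The within-arm comparison reads "Changes from baseline to post-intervention will be analyzed using paired t-tests", with the Wilcoxon signed-rank test as the alternative. Under Secondary Outcome Analysis the text is conditional: "If secondary outcomes are included, similar statistical methods will be applied as appropriate based on the type of data". It lists no secondary outcome. One of its examples is "ANOVA for continuous outcomes with more than two groups"; the Study Design section has two groups.

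**The concern.** The aim is to find out whether stimulation at the tongue differs from stimulation at the tragus. The recording made while the current is on bears directly on that question, yet no test is tied to it. Because the primary outcome has no stated epoch, the team could report the during-stimulation or the after-stimulation comparison once the results are known, for either LF or RMSSD.

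The second part of the concern is efficiency. Every participant supplies a resting value of the same measure minutes before treatment. The paired tests use it, but they look at each arm separately and do not compare the arms. The only test that does compare the arms is stated without a baseline term. If resting HRV predicts later HRV in the same person, that test gives up precision that the data already collected could supply.

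**Working it through.** The documents give no sample size, power, alpha, effect size or standard deviation, so there is no planned figure to reproduce. The check has four parts.

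**1. Recordings against tests**

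| Recording (Methodology) | Named in a within-arm test? | Named in the between-arm test? |
|---|---|---|
| Unstimulated, 6 minutes | Yes (baseline) | No |
| Under stimulation, 6 minutes | No | No |
| After stimulation | Yes, if this is what post-intervention means | No epoch stated |

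Three epochs are recorded and two time points are named. Two parameters × 3 epochs = 6 HRV values per participant. Two of the six, LF and RMSSD under stimulation, are assigned to no stated test. The listed methods are the independent t, Mann-Whitney, paired t, Wilcoxon signed-rank, chi-square and ANOVA across groups. None is described as a repeated-measures or baseline-adjusted method.

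**2. What baseline adjustment is worth**

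Assumptions: equal variance σ² at baseline and at the later epoch, and a within-arm correlation ρ between them of 0.5 to 0.8. The documents give no value for ρ. With n per arm, the variance of the arm difference is:

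- t-test on post values: 2σ²/n
- t-test on change from baseline: 2σ²/n × 2(1 − ρ)
- baseline-adjusted (ANCOVA): 2σ²/n × (1 − ρ²)

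The reduction from adjustment is therefore ρ² against post values. Against change scores it is 1 − (1 − ρ²)/[2(1 − ρ)] = 1 − (1 + ρ)/2 = (1 − ρ)/2.

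| ρ | Reduction against post values | Reduction against change scores |
|---|---|---|
| 0.5 | 0.5² = 25% | 0.5/2 = 25% |
| 0.7 | 0.7² = 49% | 0.3/2 = 15% |
| 0.8 | 0.8² = 64% | 0.2/2 = 10% |

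These are large-sample formulas. Estimating the baseline slope costs one degree of freedom, so in a very small trial the gain is slightly less.

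**3. What an open choice of epoch and parameter could cost**

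This part is an illustration only, at an assumed two-sided 5% per test. Two unadjusted between-arm comparisons of one parameter (during and after) give 1 − 0.95² = 9.75% chance of at least one false positive if independent. With both parameters there are four comparisons, and 1 − 0.95⁴ = 18.5%. The tests are correlated in practice. A null simulation on change scores (10,000 replicates, 15 or 30 per arm, correlation between epochs 0.5 or 0.8, LF–RMSSD correlation 0.5) gave about 9.0% to 9.6% and 16% to 17%.

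**4. What post-intervention means**

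The Project Summary places the effect after 30 minutes of stimulation. The Methodology section gives 30 minutes in the chair in total. Taking off the 6 unstimulated minutes leaves 30 − 6 = 24 minutes for stimulation and the final recording together, so the two statements cannot both hold as written.

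**The case against.** Several points can fairly be made for the plan.

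- **The data are not excluded.** A reader might infer that the under-stimulation recording is collected and discarded. The text does not say so. The primary outcome has no epoch, and the open-ended secondary clause could cover these values with the same two-group test. What stands is that no stated test names them.
- **The ANOVA clause is not a planned error.** A reader might infer that the three epochs will be analysed as three independent groups, with inflated standard errors. The plan offers ANOVA only as an example, for secondary outcomes that may not exist, and for more than two groups. Its stated within-arm tests are paired and respect the within-person correlation. No loss should be charged to a misuse the plan does not describe.
- **The unadjusted test is valid.** Under randomisation a two-group t-test is unbiased, so the baseline point concerns precision and not bias. That is correct, and the reductions shown above are efficiency figures.
- **Three epochs do not require a mixed model.** This also stands. Separate baseline-adjusted comparisons at each later epoch close the gap equally well. Nor should a reader expect a power gain from pooling the two later epochs. Such a gain belongs to their average, which is not the contrast proposed as primary, and averaging can lose power if the effect differs between epochs.

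The objection that remains is that much of this follows from the undefined primary outcome. That is partly so, but defining the outcome alone would still leave the stated between-arm test without a baseline term.

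**Conclusion.** The concern holds in a limited form. The under-stimulation recording has no stated role, and the stated between-arm test leaves the baseline recording unused. The first part rests on the text alone. The size of the second depends on an assumed correlation: for ρ from 0.5 to 0.8, the variance of the arm contrast falls by 25% to 64% if the intended test is on post values, and by 25% to 10% if it is on change scores. The plan does not say which is intended. The false-positive figures illustrate why one epoch and one parameter should be fixed in advance; the conclusion does not depend on them.

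The documents do not support the stronger readings that the plan excludes the under-stimulation data, that it would analyse epochs as independent groups, or that its t-test is biased. The change is worth making because it uses data already being collected.

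**What to change.** In the Statistics section, under Primary Outcome Analysis, replace the between-arm t-test with a baseline-adjusted comparison of arms for each HRV parameter. Either of two forms will do:

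- an ANCOVA at each later epoch, with arm and the baseline value as terms; or
- one repeated-measures model with arm, epoch, arm-by-epoch, baseline and baseline-by-epoch terms, and an unstructured within-person covariance. The baseline-by-epoch term and the unstructured covariance matter: a common baseline slope with a single pooled variance would let one epoch affect the precision of the other.

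Name the after-stimulation arm contrast as primary, in line with the timing in the Project Summary, and the under-stimulation contrast as secondary. State which of LF or RMSSD is primary, or how multiplicity across the two is controlled. Use a log scale only if the distributions call for it.

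The Project Summary and the Methodology section must also be reconciled on stimulation and session length, so that post-intervention has one meaning.

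The cost is revised wording and slightly more analysis work. No extra participants or recordings are needed.

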#### **Statistics**

**Descriptive Statistics:** 

Demographic and baseline characteristics will be summarized using means, standard deviations, medians, and interquartile ranges for continuous variables, and frequencies and percentages for categorical variables.

Primary Outcome Analysis:

The primary outcome will be analyzed using an independent t-test (or Mann-Whitney U test if data are not normally distributed) to compare the intervention and control groups. Changes from baseline to post-intervention will be analyzed using paired t-tests (or Wilcoxon signed-rank tests if data are not normally distributed) within each group.

Secondary Outcome Analysis:

If secondary outcomes are included, similar statistical methods will be applied as appropriate based on the type of data (e.g., chi-square tests for categorical outcomes, ANOVA for continuous outcomes with more than two groups).

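### The between-group test of LF and RMSSD ignores the baseline recorded in every participant; one prespecified baseline-adjusted ANCOVA per parameter would be more precise at no data cost

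*Combined protocol and SAP*

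**What the plan says.** The question is comparative. The Project Summary sets out to "evaluate and compare the effects on two parameters of Heart Rate Variability", and the Aims ask whether tongue stimulation "is different than trigeminal stimulation performed bilaterally at the level of the tragus".

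The Methodology gives three recordings. The first is a baseline: "For the first 6 minutes of recording, the photoplethysmographic wave of HRV in the absence of stimulation will be calculated". The second is taken during stimulation: "HRV under stimulation for another 6 minutes will be re-evaluated again". The third follows switch-off: "HRV wave after stimulation will be evaluated for the last time". Two parameters come from each: "The photoplethysmographic wave will assess two parameters of HRV: the Low Frequencies (LF) and RMSSD".

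Under Primary Outcome Analysis, the between-group sentence is: "The primary outcome will be analyzed using an independent t-test (or Mann-Whitney U test if data are not normally distributed". It does not say whether the test is run on a later value or on a change, on which later recording, or on which parameter. The next sentence gives the only inferential use of baseline: "Changes from baseline to post-intervention will be analyzed using paired t-tests (or Wilcoxon signed-rank tests if data are not normally distributed) within each group". No ANCOVA, regression or mixed model appears in the document, and no between-group effect estimate or confidence interval is named.

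**The concern.** Only the between-arm contrast answers the trial's question, and the plan tests it without the covariate likely to explain most about the outcome: the same parameter in the same person minutes earlier. An independent t-test or Mann-Whitney test on later values discards that information. Run on changes, it subtracts baseline with a fixed coefficient of 1, which over-corrects when the correlation is modest. Either way precision is lost, most on later values when r is high and most on changes when r is low.

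A second risk lies in interpretation. The only change-from-baseline analysis that is spelled out is done separately in each arm. This invites the conclusion that the sites differ because one arm changed significantly and the other did not, which is not a test of a difference.

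**Working it through.** **Inputs.** From the documents: two randomized parallel groups, one baseline and two later recordings, two parameters. Not in the documents, hence assumed: two-sided 5% level, equal allocation, equal variances at the two recordings, r from 0.3 to 0.8 (0 and 0.1 as a stress test), and the sample sizes and effects shown below. The plan states no figure to reproduce.

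**Step 1: large-sample variance.** Take the variance of a post-value comparison as 1. A change-score comparison then has 2(1 − r) and ANCOVA has 1 − r². ANCOVA relative to change is (1 − r²) / [2(1 − r)] = (1 + r)/2.

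| r | ANCOVA / post | ANCOVA / change | Saving in participants against the better of the two |
|---|---|---|---|
| 0.3 | 0.91 | 0.65 | 9% (post better) |
| 0.5 | 0.75 | 0.75 | 25% (tie) |
| 0.7 | 0.51 | 0.85 | 15% (change better) |
| 0.8 | 0.36 | 0.90 | 10% (change better) |

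**Step 2: power.** Assume 20 per arm, an effect of 0.6 SD and normal data. For post values the noncentrality is 0.6 × √(20/2) = 1.90 on 38 df. For changes it is divided by √[2(1 − r)]. For ANCOVA it is divided by √(1 − r²), with 37 df and averaging over chance baseline imbalance.

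| r | Post values | Change scores | ANCOVA | Gain over the better |
|---|---|---|---|---|
| 0.3 | 45.6% | 34.6% | 48.1% | 2.5 points |
| 0.5 | 45.6% | 45.6% | 55.8% | 10.2 points |
| 0.7 | 45.6% | 66.5% | 72.3% | 5.8 points |
| 0.8 | 45.6% | 83.2% | 85.9% | 2.7 points |

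At r = 0 and 0.1 ANCOVA gives 44.6% and 45.0% against 45.6% for post values, a loss of 1.0 and 0.6 points.

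**Step 3: skewed data and choice of scale.** Log-normal data were simulated with log-SD 0.4 or 0.6, 20 or 30 per arm, an effect of 0.6 log-SD and 6,000 replicates per setting. The plan's normality switch was modelled as Shapiro-Wilk p < 0.05 in either arm; the plan names no test, so this is an assumption. For log-SD 0.4 and 20 per arm:

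| r | Plan's rule on changes | ANCOVA, raw scale | ANCOVA, log scale |
|---|---|---|---|
| 0.3 | 35.2% | 45.0% | 47.5% |
| 0.5 | 45.4% | 50.6% | 54.4% |
| 0.7 | 67.2% | 68.3% | 72.8% |
| 0.8 | 82.2% | 81.7% | 85.6% |

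Across all settings, log-scale ANCOVA gained 2 to 18 points over changes and 3 to 41 over post values. Raw-scale ANCOVA gained 3 to 12 points over changes at r of 0.5 or less, but between −4 and +2 at r of 0.7 or more. With data normal on the raw scale (CV 0.3), taking logs cost 2 to 4 points against raw-scale ANCOVA. Type I error was 4.7–6.0% for the plan's rule and 4.3–5.5% for log-scale ANCOVA, so the normality switch itself does little harm.

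**Step 4: chance imbalance, post-value reading only.** With 20 per arm, r = 0.7 and a baseline difference of 0.5 SD, the null difference shifts by 0.7 × 0.5 = 0.35. The t-test's critical value is 1.96 × √(2/20) = 0.62, and the conditional SD is √(0.51 × 2/20) = 0.226. The conditional type I error is P(Z > (0.62 − 0.35)/0.226) ≈ 11.6%. An imbalance at least that large has probability P(|Z| > 0.5/0.316) ≈ 11%. Averaged over all randomizations the error remains 5%.

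**Step 5: paired tests read as a comparison.** If both sites change HRV equally and each paired test has power p, exactly one is significant with probability 2p(1 − p). This is 2 × 0.2 × 0.8 = 32% at p = 0.2 or 0.8, and 50% at p = 0.5.

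**The case against.** The planned analysis is valid. Allocation is random, the simulated type I error stays near 5%, and the plan does name a between-group test as primary, so the discordance figure in Step 5 describes a misreading that the plan does not itself commit. All of this stands, and it makes the point one of efficiency.

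The sponsor may intend change from baseline. The recordings come from one session in one chair, so a high r is plausible and the gain would then be at the lower end, 10 to 15% of participants. This also stands, and it is why the gain is quoted against the better of the two analyses.

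The strongest technical objection is scale. On log-normal data, raw-scale ANCOVA can also lose to the plan's rule on post values. In a separate simulation (8,000 replicates, r = 0.3) the rule on post values against raw ANCOVA gave 45.5% against 42.0% (log-SD 0.6, 20 per arm), 46.2% against 45.5% (log-SD 0.4, 20 per arm) and 59.6% against 58.1% (log-SD 0.6, 30 per arm). The largest log-scale gains over post values also mix the effect of adjustment with that of changing scale. This limits the recommendation: ANCOVA on a badly chosen scale may gain nothing. It does not undo it, because log-scale ANCOVA beat both analyses in every log-normal setting examined.

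Finally, the unnamed primary parameter and recording are the more basic gap. They are, and they should be settled in the same edit, but naming them would still leave the comparison unadjusted.

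**Conclusion.** The concern holds. The between-group comparison makes no covariate adjustment for a baseline that the protocol collects from everyone. The consequence is lost precision and exposure to chance imbalance, not an invalid test. Against the better of the two possible analyses, the saving is about 9 to 25% of participants for r between 0.3 and 0.8, or 2.5 to 10.2 power points at an assumed 20 per arm and 0.6 SD. These figures rest on assumed r, effect and sample size, equal variances and normality on the analysed scale. The gain in this trial cannot be computed from the documents. It would vanish, with a loss of about 1 point or less, if baseline and outcome were nearly uncorrelated. The change is worth making because it is cheap.

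**What to change.** - For each parameter, specify one ANCOVA of the outcome recording on arm and that parameter's baseline on the same scale. Report the adjusted difference, or ratio on the log scale, with its 95% confidence interval. On a given scale the arm effect is identical whether the dependent variable is the later value or the change, so the ambiguity between the two disappears.
- Fix the scale before data are seen. The log is reasonable for RMSSD and for LF as absolute power, since both are positive quantities. If LF is in normalized units, name another fixed scale.
- State which recording is the outcome. The wording of the paired-test sentence leans to the one after switch-off, but the between-group sentence names none.
- Name LF or RMSSD as primary, or give a multiplicity rule. Two unadjusted tests, if independent, carry a family-wise error of 1 − 0.95² = 9.75%. ANCOVA does not settle this.
- Keep the Mann-Whitney test as a sensitivity analysis and label the paired tests descriptive.

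The cost is SAP wording; no new data or visits are needed. The downsides are results read as ratios if logs are used, a few points of power if the scale is badly chosen, and about 1 point or less if r is close to zero.
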